## **2.2. Data collection instruments**

The study data were collected using an Arabic self-report questionnaire with five parts.

### **2.2.1. Demographic characteristics**

This section included a question for each variable: Age, gender, nationality, marital status, dialysis vintage, Kt/V, educational attainment, employment status, family status, and any comorbidities.

### **2.2.2. Quality of sleep**

The Pittsburgh Sleep Quality Index (PSQI) aims to evaluate sleep quality in clinical populations. The PSQI includes seven dimensions of sleep characteristics: subjective sleep quality (1 item), sleep latency (2 items), sleep duration (1 item), habitual sleep efficiency (3 items), sleep disturbances (9 items), use of sleeping medication (1 item), and daytime dysfunction (2 items). When the PSQI is scored, seven different scores are calculated for each component, ranging from 0 (no problems) to 3 (severe problems) (55). The PSQI shows internal consistency and a reliability coefficient (Cronbach's alpha) of 0.83 for its seven components (55). The Arabic PSQI had a Cronbach's alpha coefficient of 0.77, indicating satisfactory reliability (56). The Arabic version provided accurate and dependable outcomes within Arabic cancer communities (56). In our study, Chronbach's  $\alpha$  coefficient for the PSQI was 0.77.

### **2.2.3. Perceived stress**

The Perceived Stress Scale (PSS) assesses how stressful situations in one's life are perceived based on their unpredictability, lack of control, and feeling overwhelmed. It consists of 10 elements assessed using a 5-point Likert scale (0=never, 4=very often) that are mostly not specific to any particular subgroup.

Scores range from 0 to 40, with higher scores indicating greater perceived stress levels (57). The PSS showed internal consistency coefficients varying from 0.84 to 0.36 and a test-retest reliability of 0.85 (57). The Arabic PSS had a Cronbach's alpha coefficient of 0.80 and an intra-correlation coefficient of 0.90 for test-retest reliability, indicating satisfactory reliability levels (58). Almadi, Cathers, Mansour, and Chow (2012) (58) confirmed the suitability of PSS for Arabic individuals. The Chronbach's  $\alpha$  coefficient for the PSS was 0.76.

#### **2.2.4. Biomedical markers**

The Access Cortisol Assay-33600 and CRP Reagent-447280 protocols, which involved blood sampling, were strictly followed. The Access Cortisol Assay is a paramagnetic particle, competitive binding immuno-enzymatic assay for the quantitative determination of cortisol levels in human serum, plasma (heparin, EDTA), and urine using the Access Immunoassay Systems, aiding in the diagnosis of adrenal-related disorders (59). The CRP reagent, in conjunction with IMMAGE Immunochemistry Systems, is intended for the quantitative determination of C-reactive protein (CRP) in human serum or plasma (heparin, EDTA), aiding in the evaluation of stress, trauma, infection, inflammation, and surgery (60).

Both protocols were precise, specific, and sensitive in accurately measuring serum cortisol and C-reactive protein concentration (59, 60). It is necessary to do the serum cortisol test multiple times a day or several days (61). However, it is important to carefully consider the timing of cortisol testing because it follows a strong circadian rhythm, peaking during the first hour after waking up and decreasing throughout the day until midnight. Hence, routinely checking serum cortisol levels during the first hour after waking up is viewed as a consistent and trustworthy biological indicator (61-63).

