This method has been shown to be both possible and successful for individuals receiving hemodialysis (9, 32, 54, 65). In his ABC2 relaxation theory, Smith (2005) (31) stated that general populations should receive at least two 30-minute sessions of mind-body therapy training per week to induce relaxation, alleviate stress, and enhance overall health. Nevertheless, it has been proposed that a concise program structure with a minimum of 400 minutes could increase hemodialysis patients' health advantages (54). Based on physical assessments, there is a theory that morning serum cortisol and serum C-reactive protein levels may decrease after an 8-week period of mindfulness-based practices (1-3 times weekly, totaling 60-180 minutes) (66, 67). As a result, the experimental group participated in a 30-minute mindfulness meditation session three times per week for 8 weeks (720 minutes). Curtains were used to maintain the privacy of each participant during the intervention. Participants were instructed not to disclose any details about the intervention to those in the control group to avoid contamination. The healthcare professionals promptly addressed any possible interruptions, such as the alarm of the dialysis machine (peeps). Over eight weeks, participants were instructed to consistently practice the program at home before going to bed each night.

The researcher responsible for supervising the intervention delivery was an advanced nursing specialist with six years of nephrology nursing experience and a 4-day training course on mindfulness meditation. This researcher attended the sessions to manage any potential interruptions (e.g., machines' peeps and interruptions) and evaluate the intervention delivery and compliance using checklists produced according to Smith's protocol (54). After each session, the researcher completed the

checklist by asking the participants whether they had completed all the intervention protocol. If the participants felt discomfort, nausea, headache, muscle tension or any other uncomfortable symptoms during or immediately after the intervention sessions, the researcher informed the participants to stop the intervention to seek and provide the appropriate healthcare.

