#### **2.4. Procedure**

First, the permission from the instruments used in the study was obtained. Recruitment of participants was conducted by one of the study researchers who supervised the intervention delivery after obtaining approval from the hospital administrators to conduct the study. The list of all hemodialysis patients' names for both male and female floors, including their personal information (age, contact number, dialysis unit/room, hemodialysis shifts/days, hemodialysis access, hemodialysis starting date, and other chronic diseases) were gathered from the selected dialysis center. After that, all participants' files were checked for the last month Kt/V scores to conduct the inclusion criteria and select the study sample. The study purposes and protocol were explained to the patients in detail. Patients who agreed to participate in the study and met the eligibility criteria were asked to sign a consent form. Participants then completed the study variables' baseline measurements (T0) using the self-report questionnaires and measurements with a research assistant with a bachelor's nursing degree and 10 years of nephrology nursing experience. Another study researcher with a PhD degree, who was not involved in the recruitment process and data collection, randomized the participants to the experimental group ( $n = 34$ ) or the control group ( $n = 34$ ), using a simple 1:1 computer-generated sequence. The study variables were measured four weeks post the

start of the intervention (immediately after the twelve session, T1) and at the end of the final session (T2) for both groups. The measurements of the study variables at T0, T1 and T2 were conducted by the same research assistant who was not involved in any other parts of the study and blinded to randomization allocation. All measurements were privately taken at the dialysis center.

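### Cortisol timing is unreconciled: the plan argues for the waking hour, but its only stated timing puts T1 and T2 right after a mid-dialysis session, or fixes no draw time

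*Protocol*

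**What the plan says.** Section 2.2.4 explains why cortisol timing matters. The hormone is described as "peaking during the first hour after waking up and decreasing throughout the day until midnight". The section says "It is necessary to do the serum cortisol test multiple times a day or several days" and then concludes that "routinely checking serum cortisol levels during the first hour after waking up is viewed as a consistent and trustworthy biological indicator". It does not say that this trial's samples were taken in that window.

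Section 2.3.1, in justifying the length and frequency of the programme, cites a theory that "morning serum cortisol and serum C-reactive protein levels may decrease after an 8-week period of mindfulness-based practices". It places the 30-minute session for the intervention group from the end of the first hour of dialysis to the end of the second. It also adds home practice: "Over eight weeks, participants were instructed to consistently practice the program at home before going to bed each night".

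Section 2.3.2 gives the control group 30 minutes of eyes-closed rest during dialysis, with timings described as similar to those of the experimental group. The explanation that follows concerns session length. The experimental group was moved to different units for the eight weeks.

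Section 2.4 gives the only operational timing. The study variables were measured four weeks after the "start of the intervention (immediately after the twelve session, T1) and at the end of the final session (T2) for both groups". T0 follows consent and precedes randomization. All measurements were made at the dialysis center. The patient list used for recruitment included "dialysis unit/room, hemodialysis shifts/days, hemodialysis access, hemodialysis starting date", and no section restricts the draws to morning shifts.

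**The concern.** The protocol treats cortisol as an outcome whose meaning depends on when it is drawn, and points to a window soon after waking. The schedule it then gives does not fit that window. It ties the two post-baseline measurements to the end of a session, while baseline is tied to nothing.

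What is at stake is how a group-by-time result for cortisol would be read. The introduction says that cortisol rises about 15 minutes after a stressor and stays raised for several hours. So, on the protocol's own account, the hormone can move on the time scale of one session. If both post-baseline draws directly follow a session, a lower value in the meditation arm could be a short-lived response to the session just finished, a lasting change after weeks of practice, or both. The introduction and section 2.3.1 invite the lasting interpretation.

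**Working it through.** **Schedule.** Three sessions a week (section 2.3.1) give 3 × 4 = 12 sessions by week 4 and 3 × 8 = 24 by week 8. Then 24 × 30 = 720 minutes, which is the protocol's own total. T1 at the twelfth session and T2 at the last are therefore consistent with the programme.

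**Draw time on the literal reading.** The slot runs from minute 60 to minute 120 of dialysis.
- Earliest end of a 30-minute session: 60 + 30 = minute 90.
- Latest end: minute 120.
- Window supported in section 2.2.4: 60 minutes after waking.

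Since 90 > 60, a draw directly after the session misses the window even for a patient who woke at the moment dialysis began. If the slot is read loosely as any time in the first two hours, the earliest end is minute 30. Waking, travel and connection before dialysis still make a waking-hour draw implausible. If *session* in section 2.4 means the dialysis session, the draw is later still.

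**What the contrast contains.** For T1 and T2, each against T0, write the between-arm cortisol contrast as C = A + S + D:
- A is any immediate effect of meditation beyond eyes-closed rest.
- S is the effect built up over the weeks of practice.
- D is any between-arm difference due to clock time or dialysis hour.

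Even if D = 0 at both points, C1 = A1 + S1 and C2 = A2 + S2 are two equations in four unknowns. If the immediate effect is also constant (A1 = A2), then C2 − C1 = S2 − S1. That shows build-up between week 4 and week 8, but not the size of S at either point. The control arm removes the effect of resting, not A.

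**Is D zero?** The documents do not settle it. Section 2.3.2 explains similar timings by equal 30-minute duration. The second-hour slot is stated for the intervention group only. The intervention group changed units, and nothing is said about whether shifts were kept.

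**Baseline.** T0 precedes randomization, so it follows no study session. Its clock time and dialysis hour are not stated, and whether they match T1 and T2 is unknown.

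**Milestone reading.** If section 2.4 only names the visit, A need not enter. But then no draw time is stated for cortisol at T0, T1 or T2.

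**The case against.** The strongest reply is that no rule is broken. Section 2.2.4 reports a cited view and gives no sampling instruction. Its remark on repeated testing does not clearly require repeats at each time point, because T0, T1 and T2 already fall on different days. Section 2.4 gives one timing for all study variables, questionnaires included, which fits a visit milestone as well as a blood-draw rule. The stated aim is the effect on cortisol levels and does not separate a lasting from an immediate effect. The remark on morning cortisol serves to justify the programme. A between-arm contrast after the final session is still a valid contrast at that moment.

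Much of this stands. It rules out saying that the sampling was wrong, and it makes the mixing of immediate and eight-week effects conditional on the literal reading. It does not remove the need to reconcile the sections. On one reading the schedule conflicts with the rationale offered for it; on the other, the protocol stresses timing and then fixes none.

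A reader might infer two stronger claims, in opposite directions. One is that the arms were sampled at different times and the comparison is biased. No section shows that. The other is that time-of-day and dialysis-hour effects cancel because control timings were similar. That is not supported either, since similarity is explained only as session length. Nor do the documents give draw times, a cortisol standard deviation or an immediate effect of meditation, so no bias or loss of precision can be quantified.

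**Conclusion.** The point holds as a conflict within the protocol about when cortisol is measured. It should be fixed. It affects one of four outcomes: sleep quality, perceived stress, cortisol and C-reactive protein. It does not extend to the questionnaires, and the documents give no basis for a response of C-reactive protein within minutes.

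Its size can be stated only as timing: about 90 to 120 minutes into dialysis on the literal reading, against a 60-minute window after waking. That the contrast mixes an immediate with an eight-week effect rests on two assumptions: section 2.4 is a draw rule, and cortisol can respond to meditation within a session. The introduction makes the second plausible but describes a rise after stress, not a fall after meditation. If section 2.4 is only a milestone, what remains is an unfixed draw time. Confidence is moderate because the documents do not decide between the two readings.

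**What to change.** Reconcile sections 2.2.4, 2.3.1 and 2.4 by stating one research draw point for cortisol:
- the same at T0, T1 and T2 and in both arms;
- before that day's dialysis and session, at a visit patients already attend;
- at a constant clock time for each patient as far as the shift allows.

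Record waking time and draw time at each draw, and state whether shift and dialysis hour were kept alike between arms. Drop the waking-hour rationale if the draw does not meet it.

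**If the draws are already done** (section 2.1 describes a completed study), report actual draw times by arm and time point. If they followed a session, limit the conclusion to post-session cortisol. If they did not, correct section 2.4. The cost is then reporting only.

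**Cost of the prospective change.** It adds two recorded times per draw. Draws before sessions 12 and 24 reflect 11 and 23 supervised sessions: 11 × 30 = 330 of 360 minutes (91.7%) and 23 × 30 = 690 of 720 minutes (95.8%). Cortisol would also be taken earlier in the visit than measures collected after the session. Using the next visit instead keeps the full session count but moves the draw by two or three days, and T2 could then fall after the eight-week separation of units. A pre-dialysis draw may still miss the waking hour. It removes the effect of a session ended minutes before, but not that of the previous night's home practice, which lies hours back.

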## **2.3. Intervention**

### **2.3.1. Experimental group**

The experimental group received the Smith's version of mindfulness meditation (31), a standardized theory-based intervention found to be effective in improving stress and its related health problems. Smith's version of mindfulness meditation (31) comprises the following components.

(1) Being mindful of breathing, which includes easily taking in a full, deep breath, filling the lungs, simply exhaling, and then breathing naturally. It also includes noticing and simply attending to the air as it flows in and out of the nose and moves deeper into the throat and lungs (5 min).

(2) Being mindful of the body includes attending to how the body feels from head to toe and noticing any sensations that come and go. Upon noticing a sensation, the individual must gently note it, let it go, and continue attending to how the body feels (5 min).

(3) Being mindful of thought includes attending to the mind as thoughts come and go. Whenever a thought or feeling comes to mind, the individual should notice it, let it go, and continue attending to the mind repeatedly (5 min).

(4) Being mindful of sounds includes attending to the sounds one hears without thinking about them. The individual must gently notice the sound, let it go, and continue waiting (5 min).

(5) Being mindful of taste, which includes imagining a wonderful bowl of pieces of one's favorite fruit and simply attending to a taste sensation without thought, analysis, or effort (5 min)

(6) Full meditation includes gently opening one's eyes and being mindful of the world of the moment, quietly attending, and waiting. When noticing something, be it a sight,

sound, thought, or sensation, the individual must let it go and then resume attending, doing nothing else, and waiting for what comes next (5 min).

The participants in the intervention group underwent a 30-minute mindfulness meditation program three times a week for eight weeks, scheduled during their dialysis sessions, specifically between the first and second hour of hemodialysis (64). The program is based on ABC2 theory and incorporates mindfulness meditation techniques, a standardized intervention that has been proven effective in reducing stress and associated health issues (31). The researcher in the study documented the intervention guidelines in Arabic following the protocol Smith (2005) outlined. Following that, two psychologists and meditation experts approved the intervention contents, which were recorded in audio format. Following this, the recorded audio instructions were forwarded to the IT developer for assessment of the intervention program based on functionality, design, user-friendliness, and voice quality. The IT technician was on standby to address any technical issues promptly.

The participants were required to finish a 2-hour introductory course conducted in a private setting by the certified researcher before starting the training sessions in a room in the dialysis center. The introduction course educated the participants on the fundamentals, advantages, procedures, and ways to reach the intervention. Next, the recorded audio instructions were dispatched to the participants through WhatsApp and email to guarantee the uniform administration of the intervention. Participants followed the recommended instructions accessed via their cell phones and headsets during hemodialysis sessions, as documented (9, 54). The individualized intervention was provided and supervised directly at the patients' chairside while they were receiving hemodialysis treatment. The intervention delivery

using audio-recorded instructions allowed the researcher to introduce individual intervention sessions for up to five participants simultaneously.

This method has been shown to be both possible and successful for individuals receiving hemodialysis (9, 32, 54, 65). In his ABC2 relaxation theory, Smith (2005) (31) stated that general populations should receive at least two 30-minute sessions of mind-body therapy training per week to induce relaxation, alleviate stress, and enhance overall health. Nevertheless, it has been proposed that a concise program structure with a minimum of 400 minutes could increase hemodialysis patients' health advantages (54). Based on physical assessments, there is a theory that morning serum cortisol and serum C-reactive protein levels may decrease after an 8-week period of mindfulness-based practices (1-3 times weekly, totaling 60-180 minutes) (66, 67). As a result, the experimental group participated in a 30-minute mindfulness meditation session three times per week for 8 weeks (720 minutes). Curtains were used to maintain the privacy of each participant during the intervention. Participants were instructed not to disclose any details about the intervention to those in the control group to avoid contamination. The healthcare professionals promptly addressed any possible interruptions, such as the alarm of the dialysis machine (peeps). Over eight weeks, participants were instructed to consistently practice the program at home before going to bed each night.

The researcher responsible for supervising the intervention delivery was an advanced nursing specialist with six years of nephrology nursing experience and a 4-day training course on mindfulness meditation. This researcher attended the sessions to manage any potential interruptions (e.g., machines' peeps and interruptions) and evaluate the intervention delivery and compliance using checklists produced according to Smith's protocol (54). After each session, the researcher completed the

checklist by asking the participants whether they had completed all the intervention protocol. If the participants felt discomfort, nausea, headache, muscle tension or any other uncomfortable symptoms during or immediately after the intervention sessions, the researcher informed the participants to stop the intervention to seek and provide the appropriate healthcare.

### **2.3.2. Control group**

The participants in the control group were instructed to sit with their eyes closed and relaxed for 30 min three times a week for eight weeks during hemodialysis sessions to control for the nonspecific effects of social interaction and environment (Rausch et al., 2006). The timings of the control group sessions were similar to those of the experimental group, whereby if a given experimental group intervention lasted for 30 min, the control group participants would also be asked to sit with their eyes closed and relax for 30 min.

To avoid contamination bias, the experimental group participants were instructed to refrain from discussing any details about the intervention with anyone else throughout the duration of the study. The nurses and doctors at the hemodialysis center were not informed about the experimental group's intervention to avoid sharing details with the control group participants. During the study, the control group participants were given a placebo intervention, which involved closing their eyes and relaxing for 30 minutes. The experimental group participants' hemodialysis sessions were rescheduled to different units from the control group for eight weeks to prevent contamination bias during the intervention period. The participants from the experimental and control groups were allocated to separate hemodialysis units within the hemodialysis treatment center. Approval was obtained from the participants before managing the rescheduling with the nurses and physicians at the hemodialysis

center. The privacy and confidentiality of the participants were upheld by ensuring that no one could observe the data collection and intervention sessions through the use of curtains around each participant. At the end of the intervention, the researcher overseeing the intervention delivery confirmed with the control group participants that they had not engaged in or been provided with any information on mindfulness meditation throughout the study.

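### The control condition is said to hold environment and social interaction equal, but the arms are treated in separate dialysis units after baseline, and matched contact for controls is not demonstrated.

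*Protocol*

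**What the plan says.** Protocol section 2.3.2 has controls rest for 30 minutes, three times a week for eight weeks, during dialysis. The stated purpose is "to control for the nonspecific effects of social interaction and environment". The section also calls the rest a placebo: "the control group participants were given a placebo intervention, which involved closing their eyes and relaxing for 30 minutes". Session length follows the experimental arm, and "the control group participants would also be asked to sit with their eyes closed and relax for 30 min".

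The same section reports that the experimental participants' dialysis sessions were "rescheduled to different units from the control group for eight weeks to prevent contamination bias". It adds: "The participants from the experimental and control groups were allocated to separate hemodialysis units within the hemodialysis treatment center". Privacy in both arms was kept "through the use of curtains around each participant".

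For the experimental arm, section 2.3.1 describes participants as "required to finish a 2-hour introductory course conducted in a private setting by the certified researcher". It also describes supervision at the chairside, the researcher's attendance at sessions, and a checklist completed after each session by questioning the participant. For controls, apart from the instruction or request to rest, whose source is not given, section 2.3.2 describes one researcher contact, a single check once the eight weeks were over: "the researcher overseeing the intervention delivery confirmed with the control group participants that they had not engaged in". That check concerned any exposure to mindfulness meditation.

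Section 2.4 gives the order: T0, then randomization, then T1 after the twelfth session and T2 at the end of the final session. Section 2.5 names a mixed repeated-measures ANOVA as the main analysis.

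**The concern.** A control condition can support a claim specific to meditation only if the other features of care that could move the outcomes are the same in both arms. Section 2.3.2 claims this for two features, environment and social interaction. Its own description contradicts the first and does not establish the second.

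What is at stake is the meaning of a positive result. The introduction states the aim as the effectiveness of mindfulness meditation and foresees advice to the Ministry of Health on hospital use. Together with the placebo label and the stated purpose of the rest, this invites a reader to credit any group-by-time difference to meditation itself. Sleep quality and perceived stress are self-reported, and participants know what they are doing during the sessions. Setting, attention and expectation can therefore all contribute.

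**Working it through.** **Environment: the sequence of events**

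1. T0 is measured before randomization (section 2.4), so no unit separation by study arm exists yet.
2. After allocation the arms are in different units for eight weeks (section 2.3.2).
3. At three sessions a week, the twelfth session ends week 4 and the final session ends week 8. Both T1 and T2 fall within the separated period.
4. Write the expected change from T0 in the experimental arm as (time) + (programme) + (experimental units), and in controls as (time) + (rest) + (control units). The difference is (programme − rest) + (experimental units − control units).
5. No unit contains patients of both arms, so the data cannot split that sum. Randomization does not help, because the separation follows allocation. With several units per arm, a random unit term could reflect variation between units, but it still could not remove a systematic difference between the two sets of units.

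**What is and is not matched, as described**

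| Feature | Experimental arm | Control arm |
|---|---|---|
| Center, in-dialysis setting, curtains | yes | yes |
| Session time | 3 × 8 × 30 = 720 min (the figure stated in section 2.3.1) | 3 × 8 × 30 = 720 min |
| Outcome assessor | same research assistant | same research assistant |
| Dialysis unit | separate | separate |
| Introductory course | 2 hours, led by the researcher | none described |
| Supervision and attendance at sessions | described | not described |
| Checklist questions after sessions | after each session | not described |
| Request to rest | not applicable | made, but by whom is not stated |
| End-of-study check on exposure to meditation | not described | one |

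**Size: an illustration on assumed inputs**

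The documents give no unit effect, so a range is assumed. Let the systematic unit difference be d, in SD of a change score, with no programme effect. For a two-sided 5% t-test with n per arm, df = 2n − 2 and the noncentrality is d × √(n/2). With n = 34 (section 2.4), df = 66, the critical value is 1.997 and √17 = 4.123.

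| d (assumed) | noncentrality | probability of a significant result |
|---|---|---|
| 0 | 0 | 5.0% |
| 0.1 | 0.412 | 6.9% |
| 0.2 | 0.825 | 12.8% |
| 0.3 | 1.237 | 23.0% |

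Section 2.1 speaks of fifty-six recruited patients. With 28 per arm (df = 54) the last three rows become 6.6%, 11.4% and 19.7%, so the picture is the same. A single change score simplifies the three-time-point ANOVA.

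**The case against.** The strongest case on the other side has four parts.

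- **Separation has a good reason, and it is disclosed.** Section 2.3.2 gives the reason (contamination). This stands. The point does not fault the separation. It faults the claim that environment is controlled despite it.
- **The clause states a purpose, and much is shared.** Center, dialysis setting, session length, frequency and timing, curtains and the assessor are common to both arms. This stands too, and it is why the clause can be narrowed instead of deleted. None of these shared features equalizes the unit. It is also true that nowhere does the protocol say that an effect will be reported as net of setting and contact. That reading is an inference from the clause, the placebo label and the aim.
- **The contact half rests partly on silence.** This largely stands. A reader might infer that controls had almost no researcher contact, and might try to put a ratio on it. The text does not support that. Controls were instructed to rest, apparently at each session, and T1 and T2 are timed by sessions for both groups, so someone may well have been present. Any count would depend on whether those requests are included. What can be said is that matching is not demonstrated.
- **The error rates are generic, and rewording does not change them.** This stands. Any bias of the same size would give the same figures. A reader might also picture one unit per arm and derive larger figures from random unit variation. The number of units is not stated, and section 2.1 lists separate male and female wards, which makes one unit per arm doubtful. Such figures are not used here.

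**Conclusion.** The point holds, with different strength in its two halves.

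**Environment: firm.** On the protocol's own description, unit is confounded with arm from randomization through T2. Control of environment, as stated, is not a property of the design. This conclusion needs no assumed number.

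**Social interaction: not demonstrated.** The course, supervision and per-session checklist are described for the experimental arm only, and contact with controls is under-described. The documents do not show that controls lacked comparable contact. If the course and home practice count as part of the intervention, as the text suggests, the comparison is programme versus rest. It then cannot also be meditation net of contact.

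**Size: unknown.** The 6.9% to 23.0% range rests on an assumed systematic shift of 0.1 to 0.3 SD, 34 per arm and a single change score. It shows what a modest unit difference could do. It is not an estimate of this trial's type I error, and a reader should not infer that the result is invalid. What changes is what the result can be attributed to.

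**What to change.** Change the text in three places.

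1. In section 2.3.2, limit the purpose of the seated rest to what is matched: the length, frequency and timing of in-dialysis sessions at the same center. Say who asked controls to rest and who was present. If contact was in fact matched, describe it there.
2. Define the comparison, and word the conclusion, as the whole programme (introductory course, supervised sessions and home practice, delivered in separate units) versus seated rest. Do not describe an effect as meditation net of environment and contact.
3. State the number of units per arm, and state that unit is confounded with arm as the accepted price of avoiding contamination.

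The cost is wording only, with no change to patients, visits, scheduling, staff, sample size or the main test. The downside is a less specific conclusion. The rewording does not remove the confounding. It makes the stated conclusion match what the design can support.
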